No, this clinical is not a clinical trial, or does not meet the definition of an Applicable Clinical Trial, or does not need to be registered under the terms and conditions of an award, or is not a clinical trial with results intended to be reported in an journal belonging to the ICMJE. Registration is not required.

Section B: Exempt Request**B. Exempt From IRB Review**

Not Applicable

Section C: Background Information

It has been estimated that approximately 10% of people will experience foot pain in their lifetime, resulting in approximately 600,000 outpatient visits annually. The economic burden of plantar fasciitis in 2007 was estimated to be \$192 million to \$376 million indirect costs. Few studies including ours (Wrobel et al, JAPMA, 2015) suggested that orthoses provide short-, intermediate-, and long-term benefits for decreasing pain and improving function in plantar fasciitis. However, the acceptability of conventional orthoses is limited and often are costly. Furthermore, very few studies explored the benefits of footwear intervention in improving function including daily physical activities, gait, and balance.

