The Orthofeet shoes were first created in 1984 by engineers to combine attractive footwear styling with innovative therapeutic features. The shoes contain anatomical orthotic insoles that have helped millions of users improve mobility, enhance comfort from heel to toe, and get relief of heel, foot, knee, and lower pain. The insoles provide arch support with super cushioning with a mild rocker design. The shoes may reduce pressure under the heel and soften your step while you walk.

Section D: Purpose and Objectives

The purpose of this prospective proof of concept study is to examine effectiveness of a new pain relief footwear (Orthofeet) on function and daily activities over short (one week) and intermediate (6 weeks). We hypothesize a reduction in foot pain might lead to an increase in daily physical activities, measured objective using validated wearables (PAMSys and Garmin wrist watch) and functional performance (gait and balance). In addition, we hypothesis that reduction in foot pain is associated with reduced physiological stress response (HRV) and better community engagement (assessed by life space questionnaire).

Section E: Protocol Risks/Subjects

E1. Risk Category

Category 1: Research not involving greater than minimum risk.

E2. Subjects

Gender:

Both

Age:

Adult (18-64 yrs), Geriatric (65+ yrs)

Ethnicity:

All Ethnicities

Primary Language:

English

Groups to be recruited will include:

Patients

Which if any of the following vulnerable populations will be recruited as subjects?

Vulnerable populations require special protections. How will you obtain informed consent, protect subject confidentiality, and prevent undue coercion?

E3. Pregnant woman/fetus

Will pregnant women and/or fetuses (as described in 45 CFR 46 Subpart B) be enrolled in the research?

No

E4. Neonates

Will neonates of uncertain viability or nonviable neonates (as described in 45 CFR 46 Subpart B) be enrolled in the research?

No

E5. Children

Will children be enrolled in the research?

No

Section F: Design/Procedure

F1. Design

Select one category that most adequately describes your research:

c) Pilot

Discuss the research design including but not limited to such issues as: probability of group assignment, potential for subject to be randomized to placebo group, use of control subjects, etc.

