The study will be performed at the Baylor College of Medicine. Approval from Site Review Authority will be obtained. Subjects will be recruited from outpatient clinics at Baylor College of Medicine.

We propose a randomized crossover trial (Phase I/II) to evaluate acceptability as well as short (1 week) and intermediate (6 week) benefits and effectiveness of Orthofeet in reducing foot pain, increasing daily physical activities, and improving functional performance in ambulatory patients suffering from foot pain.

We are proposing a clinical study at the Baylor College of Medicine, to evaluate short and intermediate benefits and effectiveness of a novel pain relief footwear, called Orthofeet. This is a randomized crossed over trial. The duration of the study would be 12-week. We will recruit 50 eligible ambulatory adults (age 50 years or older) with moderate to severe self-reported foot pain. Participants will be randomly assigned to Group A (25 subjects) and Group B (25 subjects). There is no difference in assessments or eligibility between Group A and Group B, the only difference is when they have the opportunity to try the shoes for 6 weeks. Group A will receive a pair of Orthofeet shoes with adjustable insoles and will be asked to wear it every day activities of daily living for duration of six weeks. Participants will be also encouraged to wear the shoes inside of home if possible. Group B will be followed for duration of six weeks. At six weeks the groups will be switched and group B will receive a pair of Orthofeet shoes with adjustable insoles and Group B will follow-up for six weeks without Orthofeet shoes. Participants will be assessed at baseline, week-1, week-6, week 7, and week 12.

The primary outcome includes changes compared to baseline in foot pain intensity.

The secondary outcomes includes changes compared to baseline in various metrics of daily physical activities (e.g., daily step, longest walking bout, cadence, standing duration, and standing duration).

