Other outcomes include gait parameters (e.g., gait speed, gait steadiness, gait variability, double stance, and limp assessed using a validated wearable gait analyzer), static balance (assessed using a validated wearable balance assessment system), acceptability and perception of benefit (assessed by technology acceptance model), adherence (daily duration of wearing orthofeet), physiological stress response (e.g., heart rate variability, HRV, rest heart rate, HR-rest assessed by a wrist worn sensor), community engagement (life space assessed by a questionnaire). Standard questionnaires and assessments will be performed to evaluate subjects' perception of benefit, user-friendliness, satisfaction, adherence, pain, sleep quality, concerns for fall, frailty, moving ability, risk of falling, anxiety, and quality of life.

Resources available to conduct the Human Research

The PI is a Professor of Surgery at the Baylor College of Medicine and has been involved in multiple clinical trials along with numerous publications in the area of outcomes evaluation, foot care, pain management, physical activity monitoring, gait and balance assessments in relation to diseases such as diabetes, cancer, plantar fasciitis, and aging population. Other team members include biomedical engineers/research scientists and study coordinators who are well acquainted with the study site, culture, and society. The wearable sensor technology is available at our center (iCAMP) for this study and includes LegSys (to assess Spatio-temporal parameters of gait), BalanSens (to assess postural control) and PAMSys (to monitor daily physical activity pattern and behavior), and Garmin (to assess daily physical activities and physiological stress response). All persons assisting with the study have received appropriate training and are extremely knowledgeable in their study-related duties and functions.

Inclusion Criteria:

50 total subjects will be recruited. Those eligible will meet the following inclusion criteria: Male or female 50 years or older Self-reported foot pain including heel, arch, or ball of foot pain

Exclusion Criteria:

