Exclusion criteria: Patients with plantar ulcer Patients with major foot deformity (e.g., Charcot foot, Pes Cavus) Patients with lower extremity amputation including minor amputation. Foot pain because of nail disorder or keratotic lesions (e.g. corns, calluses) Patients with unstable conditions (e.g., recent stroke, anticipated changes in medication regime) Acute fractures of the foot Participation in an interventional Study such as exercise intervention within the last 30 days Non-ambulatory or unable to stand without help or walk a distance of at least 6 feet without assistance. Patients with major cognitive impairment or major depression Patients who are unable or unwilling to participate in all procedures and follow up evaluations

F2. Procedure

7) The research will be conducted at the following location(s): Baylor College of Medicine and Baylor St. Luke's Medical Center (BSLMC). Duration of study: 12 weeks

Research staff may contact you for any study related questions throughout your participation in the study

Visit 1 (Baseline): Maximum duration 120 minutes

Screening: Measurements will take place at your home, or in Baylor Clinic based on your preference. Participants will be randomly placed in either Group A or Group B. Group A wears the OrthoFet shoes from baseline to 6 week follow up and Group B wears OrthoFet shoes from 6 week follow up to 12 week follow up.

All the same assessments and questionnaires are completed at each visit for all participants.

Foot Pain: Foot pain will be assessed by the revised Foot Function Index (FFI). FFI was developed in 1991 to measure the impact of foot pathology on function in terms of pain, disability, and activity restriction. It is a self-administered index consisting of 23 items divided into 3 sub-scales. Both total and sub-scale scores are produced. The FFI has been shown to be a reasonable tool for use with low functioning individuals with foot disorders, patients with rheumatoid arthritis, and non-traumatic foot or ankle problems. It can be used in both clinical and research settings. Foot pain will be assessed at baseline, week-1, week-6, week-7, and week-12.

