At Visit 3 (6 Week Follow Up) the participant will complete all the same assessments and questionnaires as baseline. At this visit, Group A will stop wearing OrthoFet shoes and continue the study without them. Group B will be supplied with OrthoFet shoes to wear for the rest of their study participation until 12 Week Follow Up.

At Visit 4 (7 Week Follow Up) the participant is called by the research staff to complete the pain questionnaire, document adverse events, and answer any study-related questions.

At Visit 5 (12 Week Follow Up) the participant will complete all the same assessments and questionnaires as baseline. All participants will return OrthoFeet shoes by this point.

Section G: Sample Size/Data Analysis

G1. Sample Size

How many subjects (or specimens, or charts) will be used in this study?

Local: 50 Worldwide: 50

Please indicate why you chose the sample size proposed:

This is a proof of concept study. The sample size is 50 eligible participating in a randomized crossover study. The sample size is convenient and is selected to detect a between group difference for the primary outcome (change in foot pain) with medium effect size (Cohen's $d=0.50$) with a dropout rate of 15%, alpha of 5%, and power of 80%. The anticipated effect size was estimated from our prior study (Najafi et al, Journal of Foot and Ankle Research, 2014) in which we observed a significant drop in foot pain after orthotic therapy compared to sham orthotics. Based on this pilot study, we will propose a Phase II study to validate the observed effect in the follow-up study.

G2. Data Analysis

Provide a description of your plan for data analysis. State the types of comparisons you plan (e.g. comparison of means, comparison of proportions, regressions, analysis of variance). Which is the PRIMARY comparison/analysis? How will the analyses proposed relate to the primary purposes of your study?

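### Current Orthofeet wearers are eligible and no listed item records other footwear, so the on/off contrast may be diluted by an unknown amount

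*Combined protocol and SAP*

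**What the plan says.** **Eligibility.** The inclusion list in Section F1 reads "Male or female 50 years or older Self-reported foot pain including heel, arch, or ball of foot pain". The exclusions cover ulcer, deformity, amputation, nail and skin causes of pain, fracture, unstable conditions, ambulation and cognition. The item closest to prior treatment is "Participation in an interventional Study such as exercise intervention within the last 30 days". No item mentions Orthofeet, orthoses, insoles or therapeutic shoes.

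**Off-shoe condition.** For the first period, Section F1 says "Group B will be followed for duration of six weeks". For the second it says "Group B will follow-up for six weeks without Orthofeet shoes". Section F2, at the Week 6 visit, says "At this visit, Group A will stop wearing OrthoFet shoes and continue the study without them". The last two name different groups. Section F2 has Group B in the shoes from Week 6 to Week 12, so the Section F1 sentence needs to be reconciled with it.

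**The product and its class.** Section C says of the study shoe: "The shoes contain anatomical orthotic insoles that have helped millions of users improve mobility, enhance comfort from heel to toe", and dates it to 1984. It also reports a small number of studies suggesting that "orthoses provide short-, intermediate-, and long-term benefits for decreasing pain and improving function in plantar fasciitis", then adds that conventional orthoses are of limited acceptability and often costly.

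**What is recorded.** The outcome list in Section F1 includes adherence, defined as daily time in the study shoe. The Week 1 and Week 7 calls in Section F2 cover the pain questionnaire, adverse events and questions about the study. No item asks what other shoes or insoles are worn.

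**The concern.** The primary outcome is change from baseline in foot pain, and the comparison of interest is Orthofeet on versus off. It works as intended only if participants are not already in the study shoe, or something close to it, at baseline and in the off period.

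Two kinds of participant would break that. One already owns and wears Orthofeet: the criteria admit this person, whose baseline is already treated and whose off period may be too. The other wears an orthotic insole or therapeutic shoe, or obtains one while off the study shoe. Both would contribute little or no on/off contrast and would remain in the intention-to-treat analysis named in Section G2.

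At stake is a diluted estimate. Section G1 says a Phase II study will be proposed on the strength of the effect seen here. With footwear unrecorded, a small effect could not be separated into a weak shoe and a weak contrast.

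**Working it through.** **1. Can a current user enter and go unnoticed?**

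- Inclusion needs age 50 or over and self-reported foot pain. A current Orthofeet wearer meets both.
- No exclusion applies, because the prior-intervention item concerns taking part in another study, not shoes bought or prescribed.
- Group A is told to stop wearing the shoes at Week 6. Nothing addresses a Group B participant who has a personal pair during Weeks 0 to 6.
- Section F2 says of Week 12 "All participants will return OrthoFeet shoes by this point". It does not state that Group A hands its shoes back at Week 6.
- Adherence concerns the study shoe only. Section F2 collects chart history and a foot examination, where a prescribed orthosis might appear, but footwear is not a named item and a retail product could be missed.

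So such a participant can enter, and no listed item is designed to identify them.

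**2. The plan's own figure.** Section G1 gives 50 participants for d = 0.50, alpha 5%, power 80% and 15% dropout. Sidedness is not stated; two-sided is assumed.

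- Paired analysis, d on the within-person difference: n = ((1.960 + 0.842)/0.50)² = 31.4, so 32, or 34 by the t distribution; 34/0.85 = 40.
- Between-group comparison: n per arm = 2 × ((1.960 + 0.842)/0.50)² = 62.8, so 63, or 64 by the t distribution; 128/0.85 = 150.6, so 151.

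Neither gives 50, which Section G1 also calls a convenience size. That mismatch is a separate matter. Here the d of 0.50 serves only as the starting value.

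**3. Dilution, as an illustration.** Let q be the share of participants with no on/off difference (not in the documents), with the SD unchanged. Then d_eff = 0.50 × (1 − q). Completers are taken as 50 × 0.85 = 42.5, so 42, or 21 per arm. Power is two-sided at 5%, from the noncentral t distribution.

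| q | d_eff | Power, paired, 42 completers | Power, between groups, 21 per arm |
|---|---|---|---|
| 0% | 0.50 | 88.6% | 35.3% |
| 10% | 0.45 | 81.3% | 29.6% |
| 20% | 0.40 | 71.6% | 24.4% |
| 30% | 0.35 | 60.1% | 19.8% |

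**4. Partial effect.** If these participants keep a fraction r of the full effect, d_eff = 0.50 × (1 − q(1 − r)). With q = 20% and r = 0.5, d_eff = 0.50 × (1 − 0.10) = 0.45, rather than 0.40. The table is therefore the unfavourable end for each q.

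**The case against.** The strongest reply is that the comparator is clear enough and that the rest is a choice of question. Much of this stands.

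- *The control is undefined.* A reader might infer this from the first-period sentence alone. The documents do not support it: Sections F1 and F2 describe the off period as one without Orthofeet, and the natural meaning is the participant's own footwear. What is missing is that statement, and any record of the footwear.
- *Orthosis use is likely in this population.* No section says so. The evidence in Section C is limited to plantar fasciitis and offered tentatively, and the same paragraph says conventional orthoses have limited acceptability. Recruitment is by flyer as well as referral, and the flyer in Section R offers new shoes, which may attract few existing owners. It is not an exclusion, however.
- *Orthosis wearers should be excluded.* Comparing the shoe with whatever people with foot pain already wear is a legitimate pragmatic question. Section F1 describes moderate to severe pain, so an orthosis wearer may still have room to benefit.
- *Group B will seek other footwear while waiting, so the bias differs by group.* This is speculation. Both groups have an off-shoe period, and randomisation balances stable prior use in expectation.
- *Dilution is conservative for a claim of benefit.* True, but it does not help a pilot whose estimate is meant to inform the next study.

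The narrower point remains. The pragmatic argument does not cover people already in the study shoe itself, since for them the question of starting it does not arise.

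**Conclusion.** The concern holds in a limited form. The criteria admit current Orthofeet wearers, the off period is defined only by absence of the study shoe, and no listed item identifies people who use or start similar footwear. For such participants the on/off contrast is small or nil, and at trial level the result is dilution toward no difference.

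The size is unknown. The figures of 0.45, 0.40 and 0.35 rest on assumed shares of 10%, 20% and 30%, no effect in those participants, and an unchanged SD. The starting d of 0.50 itself comes, according to Section G1, from an orthotic-versus-sham comparison, which is not the contrast studied here.

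A reader might conclude that the whole trial becomes treated versus treated, or that a null result could not be interpreted. Neither follows. The first applies only to a subset of unknown size. A null result would still mean no detectable benefit over the footwear people were using; the difficulty is that the plan would not say what that footwear was. This is an inexpensive improvement to eligibility and data collection, not a flaw that invalidates the design.

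**What to change.** 1. Add an exclusion for current or recent users of Orthofeet footwear.
2. State in Section F1 that the off-shoe comparator is the participant's own usual footwear, and reconcile the Section F1 sentence on second-period follow-up with Section F2.
3. Record usual footwear and orthosis use at baseline. At the existing Week 1, 6, 7 and 12 contacts, ask one question: any new shoes or insoles since the last contact?
4. Add to Section G2 a sensitivity analysis by baseline orthosis use and by change in footwear, with intention to treat remaining primary. Change in footwear arises after randomisation, so that part should be read as descriptive.

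Whether to exclude wearers of other orthoses is a choice of target population for the sponsor and is not required. If they stay eligible, items 2 to 4 make the result interpretable.

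The cost is a slightly smaller recruitment pool and one extra question per contact. No visit is added, and care in the off period need not change.
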